EVALUATION PROTOCOL

Mixed method cluster randomised pilot trial of Multi-Systemic Therapy for Child Abuse and Neglect (MST-CAN) versus business as usual for families with at least one child subject to a child protection plan

The University of Kent

Principal investigator: [name]

Pilot trial protocol template (includes a control group)

Evaluating institution: University of Kent

Principal investigator(s): [name]

Project title ¹	Mixed method cluster randomised pilot trial of Multi- Systemic Therapy for Child Abuse and Neglect (MST-CAN) versus business as usual for families with at least one child subject to a child protection plan.			
Developer (Institution)	MST UK & Ireland, South London & Maudsley NHS Foundation Trust			
Evaluator (Institution)	University of Kent			
Principal investigator(s)	[name]			
Evaluation plan author(s)	[name], [name], [name], [name], [name] [name], [name]			
Evaluation setting	Family			
Target group	Families with at least one child, aged 6-17 years subject to a child protection plan.			
Number of participants 3 sites, 4 local authorities, 72 families				

Protocol version history

Version	Date	Reason for revision
1.0 [original]	17/05/24	

Table of contents

STUDY RATIONALE AND BACKGROUND	4
INTERVENTION	
RESEARCH QUESTIONS	1
SUCCESS CRITERIA AND/OR TARGETS	2
PILOT TRIAL DESIGN	3
IMPLEMENTATION AND PROCESS EVALUATION	11
OUTPUTS	15
COST DATA REPORTING AND COLLECTING	15
ETHICS AND REGISTRATION	18
DATA PROTECTION	19
STAKEHOLDERS AND INTERESTS	21
RISKS	21
TIMELINE	21
REFERENCES	22

Study rationale and background

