MST-CAN is a licensed, evidence-based intervention working with families with at least one child on a child protection (CP) plan, to reduce risks to children and support safe and effective parenting by addressing underlying barriers. MST-CAN teams include a supervisor, three therapists, a family resource specialist and input from a psychiatrist/nurse to provide an assessment of family mental health needs and support an appropriate treatment plan. Families are referred by their social worker, following a CP conference or legal planning meeting. They are introduced to the service by the MST supervisor and an allocated therapist who will work with them intensively for six to nine months. Therapists meet family members at home to seek both children and adults' views of what they want to change, assess strengths, need, and develop clear safety plans. This then contributes to an analysis of multisystemic factors contributing to abuse and neglect. Goals for treatment are developed in partnership with families and professionals. Sessions take place a minimum of three times weekly, in homes, schools or community settings, with additional contact as needed. Therapists also engage with extended family and friendship networks. An on-call rota provides 24/7 crisis support as needed throughout treatment. The family resource specialist supports families with practical barriers (e.g. finance/housing). Therapy may be individual adult or child-focused, or family-focused, depending on the clinical concern being addressed (individual, family, or community) and the priority concerns for each child and family.

Parents receive parenting and family communications skills training and couples' therapy where appropriate. If anger management is an issue for parents then CBT is provided, for

 $^{^{\}rm 2}$ At this stage the three participating centres are Flintshire and Wrexham, Leeds, and Sandwell .

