
Preconditions

The focus is on providing treatment to the entire family to overcome parenting challenges. Frontline practitioners and senior managers trained in the MST-CAN model. Ongoing regular supervision. Access to clinical input from therapists and psychiatris to play a role in delivering the intervention and supporting and supervising staff within the services. Staff are skilled in completing functional assessments, safety planning, and family needs assessment. Provision of services according to need, including parenting training, psychotherapy, anger management, family therapy and substance use treatment.

Research questions.

Research questions for the pilot trial are.

- **RQ1** To report on a two-armed cluster randomised pilot trial across three geographical areas in England and Wales.
- **RQ2** To measure pre-defined progression criteria to assess the feasibility for a definitive randomised controlled trial to evaluate efficacy
- **RQ3** To report on strategies to maximise recruitment and retention and how they should be implemented in a definitive study
- **RQ4** To report on the correlation between the primary outcome collected by parents and school to provide an indication of the most efficient method of collecting the primary outcome in a definitive trial for children aged less than 11 years.
- **RQ5** To report on the feasibility of collecting children's social care outcome data; rereferrals for child abuse and neglect, transitions from child protection to child in need, transitions from child protection to public law outline and/ or looked after child, child placed outside the family home, time on child protection register and recommend appropriate children's social care outcomes for a definitive trial
- **RQ6** To estimate the mean family size and the family intra-class correlation coefficient (ICC) to inform a sample size calculation for a definitive efficacy study.
- **RQ7** To estimate the pre- post-test correlation of the primary outcome measure to inform a sample size calculation for a definitive trial.
- **RQ8** To assess the quality of data completion at each assessment point to provide an indication of outcome measure redundancy.
- **RQ9** To provide an initial estimate of potential effect of MST-CAN versus BAU within 80% confidence intervals.
- **RQ10** To quantitively assess compliance with planned interventions in MST-CAN.

RQ11 To quantitively assess MST-CAN fidelity.

Success criteria and/or targets

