In the pilot stage of the study, we will report on the proportion of families who are eligible, consent, adhere to MST-CAN, are followed-up at the primary end point, and complete the primary and secondary outcomes. These proportions will be compared with pre-defined criteria to aid decisions regarding the feasibility of a definitive efficacy RCT.

Table 1: Proposed progression criteria

Criteria

Proportion of potential families who are eligible.	70%	50%	40%
Proportion of eligible families who consent.	70%	50%	40%
Proportion of consenting families who adhere.	80%	60%	50%
Proportion following up at month 9.	80%	70%	60%
Proportion with complete primary outcomes.	95%	85%	75%
Proportion with complete secondary outcomes.	80%	70%	60%

In addition to proportions we will assess data completeness for each outcome instrument. A threshold of 60% complete will be used to assess whether an outcome instrument should be included in any future efficacy trial.

Methods

Pilot trial design

Two-arm, mixed method cluster randomised controlled trial comparing MST-CAN versus BAU across three sites (four local authorities) in England and Wales. The unit of randomisation will be the family.

Randomisation

Randomisation will employ random permuted blocks of variable size stratified by geographical site, Wrexham and Flintshire, Sandwell and Leeds. Random strings will be created for each site and deployed independent of the research team and each family will have equal probability of being allocated to MST-CAN or business as usual.

Randomisation will be conducted once a referral has been received and after eligibility has been assessed, informed consent provided, and baseline assessment conducted. The researcher will enter necessary details into an encrypted database and after necessary data has been checked an allocation code will be provided. This code will indicate the nature of allocated group. The researcher will not be able to access randomisation codes in advance of randomisation. The participant will not be blind to the intervention.

Participants

Potential participants will be families with one or more children aged 6 to 17, subject to a Child Protection Plan for neglect, physical and/or emotional abuse in the participating local authority who meet the specified inclusion and exclusion criteria.

Inclusion criteria

- 1. Family has at least one child aged 6-17 years.
- 2. Subject to a Child Protection plan with a report of abuse or neglect in the previous 6 months.

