- 3. Usually resident in the local authority.
- 4. One parent and at least one child willing and able to provide informed consent. Consent will be taken from parents for themselves, and any child aged less than 16 years, children aged 16 years or more will provide their own consent.

Exclusion criteria

1. A child who has already been placed away from home with no prospect of reconciliation.

- 2. A child living independently.
- 3. Current actual or suspected sexual abuse involving family members.
- 4. Primary referral reason is a child's serious mental health issue.
- 5. Referred child assessed as being actively suicidal or homicidal.

Potentially eligible family referred for MST-CAN Family assessed for suitability by MST-CAN team, If ineligible family receive BAU study explained and provided with information sheet If no consent family receive Consent forms signed and BAU referred to evaluation team Evaluation team make contact and conduct baseline assessment Randomised to MST-CAN or BAU Evaluation team inform MST-CAN team and family of the allocation Evaluation team makes contact at 3 months Evaluation team makes contact at 6 months Evaluation team makes contact at 9 months and conducts follow-up assessment

Participant flow through the trial

Sample size

In the pilot study we will recruit 72 participants, 36 in each arm, across the 3 sites, with the expectation that we will successfully follow-up 58 at month 9. This will allow for exploration of key parameters needed to confirm sample size calculation for the efficacy study. It is

sufficient to allow estimation of two-sided 95% CIs around the proportions of eligible, consenting, adhering and followed-up at month 9 in each arm of the study with half-widths less than 0.15. It exceeds the 30 per group recommended by Lancaster et al (Lancaster et al., 2004) and the 35 per group recommended by Teare et al (Teare et al., 2014) for estimating the SE of a primary outcome with sufficient precision, including accounting for any variation across site, where 12 participants per arm per site is recommended.

Outcome measures

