RQ6 – We will present descriptive statistics on family composition; number of parents, children, mean age, gender, and ethnicity. We will estimate the harmonic mean (H) of family size to incorporate into a sample size calculation by estimating the design effect.

The intra-class correlation coefficient (ICC) for the primary outcome will be estimated using the following method.

ICC or $\rho = \frac{\text{Between cluster variability}}{\text{(Within cluster variability + Between cluster variability)}}$ Using statistical notation, this is depicted as: ICC or $\rho = \frac{s_b^2}{(s_b^2 + s_w^2)}$, s_b^2 = between cluster variance s_w^2 = within cluster variance

RQ7 - We will present a descriptive analysis of outcomes, including estimates of central tendency and precision, at each time-point broken down by allocated group and site. We will examine the distribution of the primary outcome, externalising behaviours at baseline and month 9 and estimate the pre- post-test correlation using an appropriate parametric or non-parametric correlation coefficient.

RQ8 - We will present the proportion of items on each outcome designated as missing at each time-point to aid an interpretation of data redundancy, if the missing data for any outcome exceeds 40%, we will explore the utility of including the outcome in any definitive trial.

RQ9 - Inferential analysis at the pilot stage will focus on the primary outcome at month 9. After conducting diagnostic plots and selecting an appropriate regression approach, adjusting for baseline values and stratification variables as covariates, we will present the marginal effect, mean difference between the MST-CAN and BAU groups and 80% confidence intervals. This analysis will provide an estimate of potential effect and aid any decision about whether conducting a definitive study is warranted.

RQ10 - Interventions delivered as part of MST-CAN will be derived from weekly case summaries currently completed by staff involved in delivering MST-CAN, a description of interventions delivered, and adherence will be provided.

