RQ11 - Fidelity in the MST-CAN group will be assessed from two perspectives, a parent completed rating of therapists, CAN-TAM, that assesses working relationships and completion of overarching goals, and a supervisor rating of fidelity (SAM) completed every two months that addresses four domains; fidelity to structure and process, adherence to principles of MST-CAN, analytical processes, and clinician development. We will present mean scores and 95% confidence intervals for each outcome at each time-point to provide an estimate of intervention fidelity.

Implementation and process evaluation

Research objectives.

A qualitative analysis will be used to address key objectives addressing the implementation, process and equity associated with the pilot. This will focus on assessing the extent to which the intervention has been implemented as intended including factors that facilitate or hinder implementation, the acceptability of the intervention from the perspectives of participants, staff and families and identify positive and negative experiences associated with the intervention and when they occur.

Research questions.

- **IPEQ1** To qualitatively explore BAU across each site.
- **IPEQ2** To qualitatively explore barriers, acceptability, implementation, and retention from the perspective of participants, practitioners, and stakeholders.
- **IPEQ3** To qualitatively explore issues relating to equality, diversity, and inclusion from the perspectives of participants, practitioners, and stakeholders.

Table 3: IPE methods overview

IPE methods overview

IPE Question	Data collection methods	Participants/ data sources (type, number)	Data analysis methods	Research questions addressed	Implementation / logic model relevance
BAU Control (IPE Q1)	Qualitative interviews with relevant stakeholders (i.e., service leads, social workers)	10-15 semi- structured interviews with stakeholders. Purposive sampling to obtain variety by site, gender identity, ethnicity	Transcription and inductive analysis to allow themes to emerge naturally	Explore the nature of and variation in BAU across local authorities	Identify what the comparison control group interventions are comprised of

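### RQ6 leaves therapist clustering in the MST-CAN arm out of the definitive design effect, and the CAN-TAM intervals in RQ11 should allow for it

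*Protocol*

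**What the plan says.** **Clustering inputs.** In the Protocol, Research questions, RQ6 is "To estimate the mean family size and the family intra-class correlation coefficient (ICC) to inform a sample size calculation for a definitive efficacy study". Under Data analysis, RQ6 puts the harmonic mean of family size into the design effect and gives a single ICC formula, between-cluster over total variance, for the primary outcome. Under Randomisation, "The unit of randomisation will be the family".

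**Size.** Sample size states "In the pilot study we will recruit 72 participants, 36 in each arm, across the 3 sites". The title table gives "3 sites, 4 local authorities, 72 families", so the 36 per arm are families.

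**Delivery.** Under Intervention, MST-CAN, families are introduced to "an allocated therapist who will work with them intensively for six to nine months". The same section says "MST-CAN teams include a supervisor, three therapists, a family resource specialist".

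**Analyses.** RQ9 leaves the regression approach to be chosen, "adjusting for baseline values and stratification variables as covariates", and reports an 80% interval. RQ11 covers CAN-TAM, in which parents rate their therapist, and says "We will present mean scores and 95% confidence intervals for each outcome at each time-point". Neither names a cluster, whether family or therapist.

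The protocol mentions therapist clustering nowhere. It gives no number of teams or therapists, no therapist ICC, and no sample size or power target for the definitive trial.

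**The concern.** A stated aim of the pilot is to estimate what is needed to design the definitive trial, and RQ6 is the question that supplies the clustering parameters. It lists the family and stops there. The protocol's own delivery model creates a second level: a few therapists each see several MST-CAN families, with at least three sessions a week over months. If therapists differ in the results they get, outcomes of families who share a therapist are correlated. The BAU arm has no MST-CAN therapist, so this component adds variance in one arm only.

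A definitive trial sized on the family-only design effect would then have less power than its calculation states. RQ11 is affected more directly, because CAN-TAM measures the therapist. Several parents scoring the same therapist are not independent observations of fidelity.

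**Working it through.** **Inputs from the protocol.** 72 families, 36 per arm, three sites, four local authorities, three therapists per team, one allocated therapist per family.

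**The plan's own figures.** 12 per arm per site × 3 sites = 36 per arm. 72 × 0.80 = 57.6, which agrees with the 58 expected at month 9. Both reproduce.

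**Families per therapist (inferred).**
- One team per site: 3 × 3 = 9 therapists, 36/9 = 4 families each. With about 29 per arm followed up, 29/9 = 3.2.
- One team per local authority: 4 × 3 = 12 therapists, 36/12 = 3 families each.

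**Assumed inputs.** The therapist ICC, ρ, is not in the protocol. I use 0.02, 0.05 and 0.10 for outcomes and 0.1 to 0.3 for CAN-TAM. The 90% power target is also an assumption.

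**Formulas, at family level with equal arms.**
- MST-CAN arm design effect: D = 1 + (m − 1)ρ, where m is families per therapist
- Variance factor for the arm difference: F = (1 + D)/2
- SE factor: √F
- Power at nominal 90%: Φ(3.242/√F − 1.960), where 3.242 = 1.960 + 1.282

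| m | ρ | D | F | √F | Power |
|---|---|---|---|---|---|
| 4 | 0.02 | 1.06 | 1.030 | 1.015 | 89% |
| 4 | 0.05 | 1.15 | 1.075 | 1.037 | 88% |
| 4 | 0.10 | 1.30 | 1.150 | 1.072 | 86% |
| 3 | 0.02 | 1.04 | 1.020 | 1.010 | 89% |
| 3 | 0.05 | 1.10 | 1.050 | 1.025 | 89% |
| 3 | 0.10 | 1.20 | 1.100 | 1.049 | 87% |

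**More than one child per family.** Take k = 2 children and an assumed family ICC ρ_F of 0.2 to 0.4. The family-only design effect is 1 + (k − 1)ρ_F. With therapists, the MST-CAN arm becomes 1 + (k − 1)ρ_F + (m − 1)kρ. At m = 4:
- ρ_F = 0.4, ρ = 0.02: (1.40 + 1.52)/2 ÷ 1.40 = 1.043
- ρ_F = 0.2, ρ = 0.10: (1.20 + 1.80)/2 ÷ 1.20 = 1.25

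So the variance of the arm difference is 4% to 25% above what a family-only design effect gives.

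**Pilot effect estimate (RQ9).** If the chosen model ignored therapists, a nominal 80% interval at m = 4 would cover 2Φ(1.2816/√F) − 1 = 79.3%, 78.4% or 76.8% for ρ = 0.02, 0.05 or 0.10.

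**CAN-TAM (RQ11).** With four raters per therapist, the SE factor is √(1 + 3ρ): √1.3 = 1.14 at ρ = 0.1 and √1.9 = 1.38 at ρ = 0.3. Replacing t on 35 df (2.030) by t on 8 df (2.306), as nine therapists would require, makes the 95% half-width 30% to 57% wider. With three raters the SE factor is √1.2 = 1.10 to √1.6 = 1.26.

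**The case against.** Family is the randomised unit, so a family design effect is right in itself, and RQ6 says only that its estimates will inform the calculation. It does not say nothing else may enter. Random effects and clustered intervals are commonly left to a statistical analysis plan, and none is shown. An assumed therapist ICC can also be applied later, when the definitive trial is designed. These points limit the finding. They do not remove it, because the protocol itself lists the clustering inputs and its list omits a level that its delivery model creates.

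A reader might infer four stronger things, which the document does not support.
- *That RQ9 and RQ11 cluster by family only, or treat observations as independent.* Neither names any cluster, and RQ9 leaves its model open.
- *That nine therapists is a fact.* The number of teams is not stated. Four local authorities could mean four teams, and staff turnover would lower the caseload further.
- *That the next trial will be undersized.* No therapist ICC, caseload or definitive sample size is given, so the shortfall is conditional.
- *That power falls to 87%, 82% or 74%.* Those figures need 12 families per therapist, which appears nowhere in the protocol.

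It can also be said that BAU families may share social workers. That may be so, but every MST-CAN family keeps a social worker too, so this would be a further level in both arms. It would not replace the therapist level in one.

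**Conclusion.** The point holds as a cheap and worthwhile improvement to RQ6 and RQ11. A family-only design effect leaves out a variance component and is too small whenever the therapist ICC is above zero. At the pilot's inferred caseload of four and assumed ICCs of 0.02 to 0.10, the effect is modest: 3% to 15% more variance in the arm difference, 1.5% to 7.2% more SE, and one to four points of power from a nominal 90%. At three families per therapist it is smaller, and at larger caseloads it grows. The CAN-TAM intervals are more sensitive, if they were computed as though parents were independent. The effect on the pilot's RQ9 interval is too small to require a change. All sizes rest on the assumed ICC ranges and the inferred number of teams.

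**What to change.** - **Data.** Record the allocated therapist for every MST-CAN family, and report the number of therapists and families per therapist. Table 2 lists no such field. The weekly case summaries are a likely source, though the protocol does not say that they identify the therapist.
- **RQ6.** Add a therapist design effect for the MST-CAN arm, 1 + (m − 1)ρ, using the observed caseload and a stated range of ρ. Nine or so therapists cannot estimate ρ precisely, so the pilot's point estimate should not be the only input.
- **RQ11.** Compute the CAN-TAM intervals clustered by therapist, with degrees of freedom based on the number of therapists.
- **RQ9.** A therapist random effect in the MST-CAN arm is optional, as a sensitivity analysis only.

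The cost is one data field, a few lines of analysis text, wider CAN-TAM intervals and a somewhat larger planned definitive sample.

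### The adherence progression criterion divides by all consenting families, half of whom are allocated to business as usual, so as written it cannot exceed about 50% and the 80% and 60% marks are out of reach

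*Protocol*

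**What the plan says.** The protocol section *Success criteria and/or targets* announces that "we will report on the proportion of families who are eligible, consent, adhere to MST-CAN", along with follow-up and outcome completion. It then says: "These proportions will be compared with pre-defined criteria to aid decisions regarding the feasibility of a definitive efficacy RCT". The adherence row of Table 1 is the "Proportion of consenting families who adhere", with marks of 80%, 60% and 50%.

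The *Randomisation* section fixes the order of events: "Randomisation will be conducted once a referral has been received and after eligibility has been assessed, informed consent provided, and baseline assessment conducted". It also states that "each family will have equal probability of being allocated to MST-CAN or business as usual". The participant flow gives the same sequence. Under *Sample size*, "we will recruit 72 participants, 36 in each arm, across the 3 sites".

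Three other places bear on the denominator:

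- *Sample size* promises 95% intervals with half-widths below 0.15 for several proportions, adherence among them, separately by arm.
- *Data analysis*, RQ2, lists adherence among the proportions to be judged against the criteria and names no arm.
- RQ10, under *Research questions* and *Data analysis*, concerns compliance within MST-CAN and draws on the weekly case summaries kept by the staff who deliver it.

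**The concern.** The numerator and the denominator describe different groups. Only families allocated to MST-CAN can adhere to it, whereas the denominator is everyone who consented, and consent is given before allocation. The first three rows of Table 1 form a chain (potential families, eligible families, consenting families) in which each denominator is the previous row's numerator. That chain works for eligibility and consent. It breaks at adherence, because randomisation comes in between and halves the group that can adhere.

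This is one of six criteria meant to inform whether a definitive trial is feasible, and the only one about take-up of the intervention. The choice of denominator changes the result by a factor of two, enough to move good adherence from above the top mark to below the bottom one. If the denominator is still unsettled when the adherence data are known, choosing it then would weaken the claim that the criteria were set in advance.

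**Working it through.** **Inputs from the protocol.** 72 families, 36 per arm; equal allocation after consent; adherence marks 80%, 60% and 50%; 58 families expected at month 9.

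**The plan's own figure.** 0.80 × 72 = 57.6, or about 58, so the expected follow-up matches the top follow-up mark in Table 1 applied to all 72 families. A denominator of 72 is right for follow-up, because both arms are followed. Adherence to MST-CAN is different.

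**Cap as written.** Maximum = families allocated to MST-CAN / consenting families = 36/72 = 50%. This takes every consenting family as randomised; any that consent but are lost before randomisation lower the cap.

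**Families needed to reach each mark.** Required count = mark × denominator, rounded up.

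| Mark | All consenting (72) | As a share of the 36 allocated to MST-CAN | MST-CAN arm only (36) |
|---|---|---|---|
| 80% | 57.6, so 58 | 57.6/36 = 160% | 28.8, so 29 |
| 60% | 43.2, so 44 | 43.2/36 = 120% | 21.6, so 22 |
| 50% | 36 | 36/36 = 100% | 18 |

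**How real adherence would be reported.**

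| Adhering in the MST-CAN arm | Result over 72 |
|---|---|
| 36/36 = 100% | 36/72 = 50% |
| 29/36 = 81% | 29/72 = 40% |
| 22/36 = 61% | 22/72 = 31% |
| 18/36 = 50% | 18/72 = 25% |

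**Could chance imbalance rescue the 60% mark?** It would take at least 44 of the 72 families allocated to MST-CAN, all adhering. Under simple 1:1 randomisation, P(X ≥ 44) for X ~ Binomial(72, 0.5) is 0.038. The protocol uses permuted blocks stratified by site, which hold the arms closer together than that, so the chance is negligible in practice. For the 80% mark, P(X ≥ 58) is about 8 × 10⁻⁸ even under simple randomisation.

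**Precision once the denominator is corrected.** Wald half-width = 1.96 × √(p(1 − p)/36):

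- p = 0.80: 1.96 × √(0.16/36) = 0.131
- p = 0.70: 1.96 × √(0.21/36) = 0.150
- p = 0.60: 1.96 × √(0.24/36) = 0.160
- p = 0.50: 1.96 × √(0.25/36) = 0.163

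The stated bound of 0.15 therefore holds at the 80% mark but not at the 60% or 50% marks.

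**The case against.** The best defence is that the intention can be inferred. Adherence is named as adherence to MST-CAN, RQ10 confines compliance to that arm, and its data source exists only there. On this view the row is a loose label, and since the *Sample size* section works arm by arm, nobody would pool the arms. Much of this is fair: the authors probably did mean the MST-CAN arm. But no sentence says so. The literal row gives another denominator, and the RQ2 analysis adds no restriction. The arm-by-arm wording argues against a pooled 72, but it cannot be squared with adherence to MST-CAN either, since it implies an adherence proportion under business as usual, for which no measure is described.

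A second defence is that a statistical analysis plan, not shown here, may settle the matter. It may, and doing so before the data are reviewed would be clarification. That does not excuse the protocol: the denominator is not left open but stated, and it does not suit its numerator.

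It is also fair that the criteria are labelled as proposed and serve only to aid a decision. No rule stops the programme on one row.

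A reader might go further and infer two things that the protocol does not support:

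- *That the pilot fails this criterion even with perfect delivery.* Perfect adherence gives exactly 50%, which equals the lowest mark. The column headings of Table 1 are missing from the text available, so what 50% signifies cannot be stated.
- *That the denominator will have to be changed after the data are seen.* That is a risk, not a certainty, because it can be corrected earlier.

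**Conclusion.** The adherence row of Table 1 is wrong as written. With 36 of 72 consenting families allocated to MST-CAN, the proportion is capped at about 50%. Two of the three marks cannot be reached, the third requires every MST-CAN family to adhere, and 81% adherence in that arm would be reported as 40%.

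This rests on the literal denominator, on adherence meaning adherence to MST-CAN, and on allocation close to the planned 36 per arm. If the MST-CAN arm was intended, the marks are sound and only the wording is at fault. The wording still has to change, because it states a decision criterion that gives the wrong answer, and the passage on precision by arm conflicts with the likely intention.

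The shortfall against the 0.15 bound at the 60% and 50% marks is a secondary point. It does not add to the seriousness of the denominator error.

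**What to change.** Before any adherence data are reviewed:

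1. Reword the row in Table 1 to *Proportion of families allocated to MST-CAN who adhere*, with a planned denominator of 36. The existing marks can stay; they become 29, 22 and 18 of 36.
2. Name the same denominator for adherence in the RQ2 analysis.
3. In *Sample size*, take adherence out of the statement on both arms and say that it is estimated in the MST-CAN arm only, with a 95% half-width of about 0.13 at 80% and 0.16 at 60%, in place of the blanket bound of 0.15.

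The cost is one line in the table and two short edits to the text. It needs no extra families and no new data, and the design does not change.

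### The Sample size section's unqualified claim of 95% CI half-widths below 0.15 in each arm fails with 36 per arm at proportions around 50% to 60%, and three of its four proportions do not exist in each arm

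*Protocol*

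**What the plan says.** The Sample size section sets the target: "In the pilot study we will recruit 72 participants, 36 in each arm, across the 3 sites". It then says this number is "sufficient to allow estimation of two-sided 95% CIs around the proportions of" families "eligible, consenting, adhering and followed-up at month 9 in each arm of the study with half-widths less than 0.15". No proportion is assumed, no interval method is named and no denominator is given. The same section expects 58 of the 72 to be followed up, and cites two published per-group recommendations (30 and 35) and a figure of 12 per arm per site.

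Three other places bear on the sentence:

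- The summary table on the first page gives the unit: "3 sites, 4 local authorities, 72 families". The Randomisation section gives equal allocation.
- Table 1 (Proposed progression criteria) sets three marks per criterion: eligibility 70/50/40%, consent 70/50/40%, adherence 80/60/50% and follow-up 80/70/60%. Eligibility is taken over potential families and consent over eligible families. The follow-up row, "Proportion following up at month 9", is not split by arm. The text introducing Table 1 describes adherence as adherence to MST-CAN.
- The Randomisation section places allocation after eligibility assessment, consent and baseline assessment. The participant flow shows the same order.

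**The concern.** Two things do not fit. First, the half-width of an interval for a proportion depends on the proportion and is widest at 50%. A bound stated without conditions must therefore hold at 50%, and 36 is too few for 0.15 there. Second, three of the four proportions cannot be estimated in each arm. Every randomised family is by design eligible and consenting, and only families allocated to MST-CAN can adhere to it.

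RQ2 compares these proportions with Table 1, and this sentence tells the funder how precise that comparison will be. A reader who relies on it would expect better precision for adherence than 36 families can give at 50% or 60%. The same reader would look for per-arm eligibility and consent rates that the design cannot produce, although the overall rates will be estimated more precisely than the sentence suggests.

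**Working it through.** **Inputs.** 72 families, 36 per arm, two-sided 95% (z = 1.96), claimed half-width below 0.15 (all Sample size section); marks from Table 1; timing from the Randomisation section. The 72 participants are taken to be families, as on the first page.

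**1. Where the stated figure reproduces.** Wald half-width = 1.96 × √(p(1 − p)/36).

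- p = 0.70: 1.96 × √(0.21/36) = 0.1497
- p = 0.80: 1.96 × √(0.16/36) = 0.1307
- p = 58/72 = 0.806 (expected follow-up): about 0.129

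The claim therefore holds at the first-column marks. The n required at 70% is 0.21 × (1.96/0.15)² = 35.9, which rounds up to exactly 36, so the sentence may have been derived at 70%. The protocol does not say so.

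**2. Where it fails.** Half-widths at n = 36:

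| Proportion | Wald | Wilson | Exact (nearest count) |
|---|---|---|---|
| 50% | 0.163 | 0.155 | 0.171 (18/36) |
| 60% | 0.160 | 0.152 | 0.167 (22/36 = 61.1%) |
| 70% | 0.1497 | 0.144 | 0.159 (25/36 = 69.4%) |
| 80% | 0.131 | 0.128 | 0.139 (29/36 = 80.6%) |

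Wilson half-width = [1.96/(1 + 1.96²/36)] × √(p(1 − p)/36 + 1.96²/(4 × 36²)). Exact means Clopper-Pearson.

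Limits of the failing band:

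- Wald: solve p(1 − p) = 36 × (0.15/1.96)² = 0.2108, so p = 0.5 ± √(0.25 − 0.2108), that is 0.302 and 0.698. This covers every count from 11/36 to 25/36.
- Wilson: 0.364 to 0.636.
- Exact: 9/36 to 27/36, that is 25% to 75%.

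The 60% and 50% adherence marks, and the 60% follow-up mark taken per arm, lie inside all three bands.

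**3. What an unconditional bound would take.** At p = 0.5 the Wald requirement is 0.25 × (1.96/0.15)² = 42.7, so 43 per arm. With 36 per arm, the bound that can be stated for every proportion is 0.163.

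**4. Right denominators.**

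- Eligibility and consent: the rates are not known, so the Table 1 marks serve as assumptions. If both are 70%, 72/0.7 = 103 eligible and 103/0.7 = 147 potential families. Half-widths are 1.96 × √(0.21/103) = 0.09 for consent and 1.96 × √(0.21/147) = 0.07 for eligibility. If both are 40%, 72/0.4 = 180 and 180/0.4 = 450 families, with half-widths 0.07 and 0.05.
- Adherence: 36 MST-CAN families, at most 0.163.
- Follow-up: 72 overall, at most 1.96 × √(0.25/72) = 0.1155; 36 per arm, at most 0.163.

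**The case against.** The strongest defence is that the sentence lacks a qualifier and contains no miscalculation. It reproduces at every first-column mark for the four proportions and at the expected follow-up. The misses elsewhere are small: 0.010 to 0.013 by Wald, and about 0.002 by Wilson at 60%. All of that is true. But the qualifier is absent, and Table 1 itself uses 60% and 50%, where the bound does not hold by any of the three methods.

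It can also be said that the per-arm phrase attaches only to follow-up, the last item in the list, and that nobody would analyse eligibility by arm when it precedes randomisation. The grammar allows this. It does not rescue the figure: follow-up in 36 families still misses 0.15 at 60%, and adherence still rests on 36 families.

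Some stronger readings are tempting, and the protocol does not support them:

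- *The trial is too small.* The precision sentence is one of several grounds for the sample size. The parameters for a definitive trial and the published recommendations stand apart from it.
- *The progression decision is undermined.* The protocol compares proportions with Table 1 and states no rule based on confidence intervals. Table 1's follow-up criterion is not per arm, and on 72 families the half-width stays well inside 0.15. Intervals wider than the 10-point gaps between marks are not caused by this error: a half-width of 0.15 already spans 30 points.
- *The claim fails everywhere between 30% and 70%.* That band is Wald's. Wilson's is narrower and the exact band is wider.

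**Conclusion.** The sentence is wrong as written and should be corrected. Taken as the unconditional bound it states, a half-width below 0.15 with 36 per arm fails at 50% by Wald, Wilson and exact limits (0.163, 0.155 and 0.171) and at or near 60% (0.160, 0.152 and 0.167). It holds by Wald at about 70% and above, or 30% and below. Separately, and whatever method is assumed, only follow-up can be estimated in each arm: the protocol's own order of events rules this out for eligibility and consent, and its own description of adherence limits that to MST-CAN.

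The effect is limited to the stated precision. It is slightly worse than claimed for adherence and for per-arm follow-up at the lower marks. It is better than claimed for eligibility, consent and overall follow-up. The eligibility and consent figures rest on assumed rates of 40% to 70%; the rest needs only n = 36 or 72 and the named interval method.

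**What to change.** Rewrite the sentence in the Sample size section so that it names the interval method and gives each proportion its own denominator:

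- Eligibility: once, among potential families. Half-width about 0.07 with 147 families if eligibility and consent are both 70%; about 0.05 with 450 families if both are 40%.
- Consent: once, among eligible families. About 0.09 with 103 families, or about 0.07 with 180, under the same two assumptions.
- Adherence: in the 36 MST-CAN families, up to 0.163 (Wald).
- Follow-up: overall in 72 families, up to 0.116, and per arm in 36, up to 0.163, or about 0.13 at the expected 80%.

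If the authors prefer to keep 0.15, they should state that it assumes a proportion of at least 70% and the Wald method, and confine the per-arm wording to follow-up. The cost is a few lines of text and a slightly less favourable per-arm figure. No extra families are needed, and Table 1 and the analysis stay as they are.
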